2. LIST OF ABBREVIATIONS

See Medicine Glossary:

website: glossary

Term	Definition / description
ALT	Alanine Aminotransferase
ANCOVA	Analysis of Covariance
AST	Aspartate Aminotransferase
[REDACTED]	[REDACTED]
AUC _{0-∞}	Area under the concentration-time curve of the analyte in plasma over the time interval from 0 extrapolated to infinity
AUC _{t1-t2}	Area under the concentration-time curve of the analyte in plasma over the time interval t1 to t2
AUC _{τ,ss}	Area under the concentration-time curve of the analyte in plasma at steady state over a uniform dosing interval τ
BLQ	Below limit of quantification
BMI	Body mass index
BMS	Biomarker Set
CI	Confidence Interval
C _{max}	Maximum measured concentration of the analyte in plasma
C _{max,ss}	Maximum measured concentration of the analyte in plasma at steady state
CSD	Company standard displays
CV	Arithmetic Coefficient of Variation
DBLM	Database Lock Meeting
DILI	Drug induced liver injury
ECGPCS	ECG Pharmacokinetic Concentration Set
FEF 25-75	Forced Expiratory Flow at 25-75%
[REDACTED]	[REDACTED]
FEV1	Forced Expiratory Volume (Pressure) in 1 second
[REDACTED]	[REDACTED]
[REDACTED]	[REDACTED]
FVC	Forced (expiratory) Vital Capacity
gCV	Geometric Coefficient of Variation

Term	Definition / description
gMean	Geometric Mean
LI	Linearity Index
LLOQ	Lower limit of quantification
LLT	Lower Level Term
IQRMP	Integrated Quality and Risk Management Plan
Max	Maximum
Min	Minimum
N	Number non-missing observations
P10	10 th percentile
P90	90 th percentile
PEF	Peak Expiratory Flow
PKS	PK parameter analysis set
Q1	1 st quartile
Q3	3 rd quartile
RAGe	Report Appendix Generator system
RV	Residual Volume
SD	Standard Deviation
sd	Single dose
SVC	Slow Vital Capacity
TS	Treated Set
ULN	Upper Limit of Normal
WHO-DD	World Health Organization Drug Dictionary

3. INTRODUCTION

As per ICH E9 ([1](#)), the purpose of this document is to provide a more technical and detailed elaboration of the principal features of the analysis described in the protocol, and to include detailed procedures for executing the statistical analysis of the primary and secondary endpoints and other data.

This trial statistical analysis plan (TSAP) assumes familiarity with the Clinical Trial Protocol (CTP), including Protocol Amendments. In particular, the TSAP is based on the planned analysis specification as written in CTP Section 7 “Statistical Methods and Determination of Sample Size”. Therefore, TSAP readers may consult the CTP for more background information on the study, e.g., on study objectives, study design and population, treatments, definition of measurements and variables, planning of sample size, randomisation.

Study data (including data entered in the RAVE EDC system and external data provided by suppliers) will be stored in a Clinical Data Repository (CDR).

The statistical analyses will be performed within the validated working environment CARE, including SAS® (current Version 9.4, by SAS Institute Inc., Cary, NC, USA), and a number of SAS®-based tools (e.g., macros for the analyses of AE data or laboratory data; Report Appendix Generator system (RAGe) for compilation/formatting of the CTR appendices).

[figure not shown]
4. CHANGES IN THE PLANNED ANALYSIS OF THE STUDY

All analyses as planned in the CTP will be performed and are described in more detail in this TSAP.

In addition, an enrolled set (ES) and an ECG pharmacokinetic concentration set (ECGPCS) have been introduced. The ECGPCS is used for the ECG exposure response analysis.

Additionally, the linearity index will be determined in the MRD part (see [section 7.6](#) for details).

In CTP Section 7.5.1 it is stated that it is not planned to impute missing values for safety parameters. Nevertheless, according to BI standards, missing or incomplete AE dates as well as missing baseline laboratory parameters will be imputed. Standards for ECG endpoint calculations are also applied (refer to [section 6.6](#) for details).

5. ENDPOINTS

5.1 PRIMARY ENDPOINT

Section 2.1.2 of the CTP: *Primary endpoint to assess safety and tolerability of BI 894416 is the percentage of patients with drug-related adverse events.*

5.2 SECONDARY ENDPOINTS

5.2.1 Key secondary endpoint

This section is not applicable as no key secondary endpoints have been defined in the CTP.

5.2.2 Secondary endpoints

Section 2.1.3 of the CTP:

Efficacy Endpoints: (for lung function and small airway assessment) from MRD part:

- Airway resistance (Raw) after 7 days of t.i.d. treatment

Pharmacokinetic Endpoints for BI 894416:

SRD part:

- $AUC_{0-\infty}$ (area under the concentration-time curve of the analyte in plasma over the time interval from 0 extrapolated to infinity)
- C_{max} (maximum measured concentration of the analyte in plasma)

[figure not shown]
MRD part:

[figure not shown]
After the first dose:

[figure not shown]
- AUC_{0-8} (area under the concentration-time curve of the analyte in plasma over the time interval 0 to 8h)
- C_{max} (maximum measured concentration of the analyte in plasma)

After the last dose:

- $AUC_{\tau,ss}$ (area under the concentration-time curve of the analyte in plasma at steady state over a uniform dosing interval τ)
- $C_{max,ss}$ (maximum measured concentration of the analyte in plasma at steady state)

6. GENERAL ANALYSIS DEFINITIONS

6.1 TREATMENTS

For basic study information on investigational products, assignment of treatments and selection of doses, please see CTP, Section 4.

The study will be performed as randomised, placebo-controlled, single-blind, parallel group study with two parts (SRD part and MRD part) in patients with mild asthma.

If not otherwise stated, the two trial parts (SRD and MRD) will be evaluated separately.

It is planned that 50 patients will be treated with a single dose of BI 894416 or Placebo in the SRD part of the trial and 50 patients will be treated up to 7 days with tid dosing and 2 days with qd dosing of BI 894416 or Placebo in the MRD part of the trial. Both trial parts consist of 5 dose groups comprising a planned number of 10 patients per group (8 on active treatment, 2 on Placebo).

Table 6.1: 1 Labels for treatments for use in the CTR – SRD part

Dose group	Sort order	Treatment	Short label
	1	P ⁺	Matching Placebo tablet q.d.
1	2	A	75 mg BI 894416 tablet q.d.
2	3	B	125 mg BI 894416 tablet q.d.
5	4	K	170 mg BI 894416 tablet q.d.
3	5	C	175 mg BI 894416 tablet q.d.
4	6	D*	225 mg BI 894416 tablet q.d.

*The dosage may be reduced to a dose >175 mg and <225 mg in case that preliminary PK analysis predict that a dose lower than 225 mg is needed to not exceed the limits of exposure

⁺The placebo group in the safety evaluation will consist of all patients treated with placebo, regardless of the dose group in which they were treated.

The SRD part was stopped after dose group BI 170mg single dose (sd) as exposure limits outlined in the CTP were reached. Dose groups BI 175mg sd and BI 225mg sd were not performed.

Table 6.1: 2 Labels for treatments for use in the CTR – MRD part

Dose group	Sort order	Treatment	Short label
	1	R ⁺	Matching Placebo tablet t.i.d.
1	2	F	10 mg BI 894416 tablet t.i.d.
2	3	G	25 mg BI 894416 tablet t.i.d.
3	4	H	50 mg BI 894416 tablet t.i.d.
5	5	L	60 mg BI 894416 tablet t.i.d.
4	6	I*	70 mg BI 894416 tablet t.i.d.

⁺The placebo group in the safety evaluation will consist of all patients treated with placebo, regardless of the dose group in which they were treated.

*The dosage may be reduced to a dose >50 and <70 mg tid in case that preliminary PK analysis predict that a dose lower than 70 mg tid is needed to not exceed the limits of exposure (CTP Section 4.1.2) or to not exceed the exposure covered by the SRD part of the trial with predicted gMean C_{max,ss} and AUC_{0-24,ss} values.

With CTP version 5.0, an interim dose group (dose group 5) of 60 mg tid is inserted between dose group 3 and 4. Dose group BI 70mg tid was not performed.

Section 1.2.2 of the CTP: ...the individual patient's end of trial is 14 days following last dosing with BI 894416 or placebo at the earliest.

All AEs reported between administration of BI 894416 and the individual patient's end of trial will be counted as on-treatment AEs.

The following separate study phases will be defined for the analyses of AEs:

- **Screening** (ranging from 0:00h (midnight) on day of informed consent until first administration time of study drug (BI 894416 or Placebo))
- **On treatment**
 - **BI/Placebo treatment** (separately for each treatment, ranging from the time of first administration of BI 894416/Placebo until 0:00h (midnight) on the day after trial completion date)

The following AE displays will be provided in the report:

Section 15.3 (separately for SRD and MRD part) and Appendix 16.1.13.1.8 (for ClinicalTrials.gov and EudraCT only but combined for SRD and MRD part) of the CTR displays:

In these displays, the on-treatment phase will be analysed (labelled with the name of the study treatment (short label)). Screening will not be included in this analysis.

The following totals will be provided in section 15.3 in addition:

- a total over all on-treatment phases ("Total")
- a total over all on-treatment phases involving BI 894416 ("BI Total")

The following totals will be provided in section 16.1.13.1.8 in addition:

- a total over all on-treatment phases ("Total")
- a total over all on-treatment phases ("Total - SRD part")
- a total over all on-treatment phases ("Total - MRD part")
- a total over all on-treatment phases involving BI 894416 ("BI Total")
- a total over all on-treatment phases involving BI 894416 ("BI Total – SRD part")
- a total over all on-treatment phases involving BI 894416 ("BI Total – MRD part")

In Section 15.4 and Appendix 16.2 (Listings) of the CTR displays the screening period will be included and no totals will be provided.

Tables of vital signs and laboratory values will present results by the above mentioned on-treatment phase.

For detailed information on the handling of the treatments refer to Technical TSAP ADS (analysis data set) plan and Analysis Data Reviewers guide.

6.2 IMPORTANT PROTOCOL DEVIATIONS

Data discrepancies and deviations from the CTP will be identified for all treated patients.

Section 7.3 of the CTP: *Important protocol deviation (iPD) categories will be specified in the iQRMP, iPDs will be identified no later than in the Report Planning Meeting, and the iPD categories will be updated as needed.*

Consistency check listings (for identification of deviations of time windows) and a list of protocol deviations (e.g. deviations in drug administration, in blood sampling times, etc.) will be provided to be discussed at the Report Planning Meeting and database lock meeting (RPM/DBLM). At this meeting, all manual deviations identified at the sites by the CRAs and deviations too complex to program will be reviewed by the trial team to decide which are considered important. For definition of important protocol deviations (iPD), and for the process of identification of these, refer to the Boehringer Ingelheim (BI) SOP "Identify and Manage Important Protocol Deviations (iPD)" (2).

If any iPDs are identified, they are to be summarised into categories and will be captured in the RPM/DBLM minutes and decision log as well as an accompanying Excel spreadsheet (3). Categories which are considered to be iPDs in this trial are defined in the integrated quality and risk management plan (IQRMP). If the data show other iPDs, the definition in the IQRMP will be supplemented accordingly by the time of the Report Planning Meeting.

The iPDs will be summarised and listed.

Table 6.2: 1 below specifies which kind of iPDs could potentially lead to exclusion from which analysis set. The decision on exclusion of patients from analysis sets will be made at the latest at the Report Planning Meeting, after discussion of exceptional cases and implications for analyses.

Table 6.2: 1 Handling of iPDs

iPD code	iPD Category & Brief Description	Excluded from which analysis set
iPD B1	Informed consent not available/not done	All
iPD B2	Informed consent too late	None
iPD B3	Wrong informed consent form signed	All
iPD A	In-/Exclusion Criteria Not Met	PKS, BMS, ECGPCS
iPD C1	Incorrect trial medication taken	PKS, BMS, ECGPCS
iPD C2	Randomisation not followed	PKS, BMS, ECGPCS
iPD C3	Wrong dosage schedule	PKS, BMS, ECGPCS
iPD C4	Incorrect intake of trial medication	PKS, BMS, ECGPCS
iPD D1	Prohibited medication use	PKS, BMS, ECGPCS
iPD D2	Improper washout of concomitant medication	PKS, BMS, ECGPCS
iPD E1	Certain violations of procedures used to measure primary or secondary data	PKS, BMS, ECGPCS
iPD F1	Certain violations of time schedule used to measure primary or secondary data	PKS, BMS, ECGPCS
iPD G1	PDs affecting efficacy, safety and rights	PKS, BMS, ECGPCS
iPD G2	Certain deviations of time schedule with respect to nutrition	PKS, BMS, ECGPCS
iPD Q1	Missed examination	PKS, BMS, ECGPCS
iPD Q2	Missed visit	PKS, BMS, ECGPCS
iPD Q3	Drug shipment	PKS, BMS, ECGPCS

6.3 SUBJECT SETS ANALYSED

Section 7.3 of the CTP: *Statistical analyses will be based on the following analysis sets:*

- **Enrolled Set (ES):**
This subject set includes all patients who were enrolled in the study regardless of whether they were treated or not. The ES is used for the disposition table / listing.
- **Treated set (TS):** *The treated set includes all patients who were randomised and treated with at least one dose of study drug. The treatment assignment will be*

determined based on the first treatment the patients received. The treated set will be used for safety analyses.

- *Pharmacokinetic parameter analysis set (PKS): This set includes all patients in the treated set (TS) who provide at least one PK endpoint that was not excluded due to a protocol deviation relevant to the evaluation of PK or due to PK non-evaluability (as specified in the following subsection 'Pharmacokinetics'). Thus, a patient will be included in the PKS, even if he/she contributes only one PK parameter value for one period to the statistical assessment. Descriptive and model based analyses of PK parameters will be based on the PKS.*
- [REDACTED]
- [REDACTED]
- ECG Pharmacokinetic Concentration Set (ECGPCS):
This subject set includes all patients from the TS who provide at least one pair of a valid drug plasma concentration of BI 894416 and a corresponding (i.e. time-matched) ECG endpoint to be used in the exposure-response analyses. For placebo patients, the plasma concentration is set to zero and hence always considered as valid. The decision whether a time deviation between PK blood sampling and ECG recording is acceptable (and thus whether the pair of values will be used) is to be made no later than at the RPM before data base lock.
All ECG analyses are performed on the TS, except for the exposure-response analyses, which are performed on the ECGPCS.

Pharmacokinetics

Plasma and urine concentration data and parameters of a patient will be included in the statistical pharmacokinetic (PK) analyses if they are not flagged for exclusion due to a protocol deviation relevant to the evaluation of PK (to be decided no later than in the Report Planning Meeting) or due to PK non-evaluability (as revealed during data analysis, based on the criteria specified below). Exclusion of a patient's data will be documented in the CTR.

Relevant protocol deviations may be

- *Incorrect trial medication taken, i.e. the patient received at least one dose of trial medication the patient was not assigned to*
- *Incorrect dose of trial medication taken*
- *Use of restricted medications*

Plasma and urine concentrations and/or parameters of a patient will be considered as nonevaluable, if for example

- *The patient experienced emesis that occurred at or before two times median t_{max} of the respective treatment (Median t_{max} is to be determined excluding the patients experiencing emesis),*
- *Missing samples/concentration data at important phases of PK disposition curve.*

Plasma/urine concentration data and parameters of a patient which is flagged for exclusion will be reported with its individual values but will not be included in the statistical analyses.

Only concentration values within the validated concentration range and actual sampling times will be used for the calculation of pharmacokinetic parameters. Concentrations used in the pharmacokinetic calculations will be in the same format as in the bioanalytical report (that is to the same number of decimal places provided in the bioanalytical report).

[REDACTED]

[REDACTED]

[REDACTED]

[REDACTED]

[REDACTED]

[REDACTED]

Table 6.3: 1 Subject sets analysed

Class of endpoint	Subject set				
	ES	TS	PKS	BMS	ECGPCS
Analysis of PK endpoints			X		
ECG endpoints and plasma concentrations used in exposure-response analysis					X
Safety parameters		X			
Demographic/baseline parameters		X			
Important protocol deviations		X			
Disposition	X				

6.5 POOLING OF CENTRES

This section is not applicable, because the study was performed in only one centre.

6.6 HANDLING OF MISSING DATA AND OUTLIERS

Handling of missing data and outliers will be performed as described in the CTP, Section 7.5.

The only exceptions where imputation might be necessary for safety evaluation are AE dates. Missing or incomplete AE dates are imputed according to BI standards (see BI-KMED-BDS-HTG-0035 (4)).

Missing data and outliers of PK/█ data are handled according to BI standards (see 001-MCS-36-472_RD-01) (5).

Missing baseline laboratory values will be imputed by the respective values from screening.

Unscheduled measurements of laboratory data or vital signs will be assumed to be repeat measurements of the most recent scheduled measurement (e.g. for follow-up or confirmation of a particular value). Therefore, unscheduled measurements will be assigned to the planned time point of the previous scheduled measurement. Adherence to time windows will be checked via the consistency check listings at the RPM/DBLM.

If single cardiac cycles of an ECG (out of the generally four) are missing, the arithmetic mean for this single ECG will be computed with the reduced (1, 2 or 3) number of cardiac cycles. If all cardiac cycles of an ECG are missing, no imputation will be done.

If replicate ECG recordings are missing, the arithmetic means per time point will be computed with the reduced number (1 or 2) of recordings.

For the classification of the on-treatment QTc/QT intervals into “no new onset” / “new onset” categories, a missing value is obtained only in case that

- (i) all on-treatment values are missing and
- (ii) the baseline value is less than or equal to 500 msec, or missing.

If condition (i) is fulfilled but the baseline value is greater than 500 msec, this case will be categorized as ‘no new onset’. If baseline is missing and the maximum on-treatment QTc interval is greater than 450 msec (or 500 msec for QT interval, respectively), this is classified as a ‘new onset’ in the respective category. If baseline is missing and the maximum QTc interval is less than or equal to 450 msec (or 500 msec for QT interval, respectively), this will be categorized as ‘no new onset’. If baseline is missing, a QTc/QT interval > 500 msec at any time on treatment will be a notable finding.

For placebo patients the missing plasma concentration values will be replaced by 0 for the exposure response analysis. For patients on active drug, missing plasma concentration values with ‘BLQ’ in the comment field will not be replaced.

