PK urine ¹³								
Adverse Events ¹⁴		X	X	X	X	X	X	X
Concomitant Therapy ¹⁴		X	X	X	X	X	X	X

O = Outpatient, I = Inhouse

1. Patient must be informed and written informed consent obtained prior to starting any screening procedures.
2. Including determination of body height and weight, smoking history and alcohol history.
3. Data are not needed to be entered in the electronic case report form (eCRF) again if already collected and entered in eCRF for a previous screening for this study within 30 days before current screening.
4. [REDACTED]
5. Vital signs must be completed prior to bodyplethysmography.
6. Letters A, B, and C describe different sets of safety laboratory examinations (see [Section 5.2.4](#))
7. Drug screening will be performed at screening and prior to dosing on Day 1 of visit 3. A breath alcohol test will be performed prior to BI 894416 or placebo administration in Visit 3, and may be repeated at any time during the study at the discretion of an investigator or designee.
8. At Day 1 the following procedures must be completed prior to BI 894416 or placebo administration: Safety laboratory, neurological examination, Vital signs, ECG, [REDACTED] and PK samplings. The respective procedures are to be performed and completed within 3 h prior to BI 894416 or placebo administration. Allocation to treatment at Visit 3 could be performed at any time following enrolment but had to be completed prior to BI 894416 or placebo administration.
9. PK samplings and ECGs should be done in direct sequence for matching reasons. Please refer to Flow Chart “[SRD part – Time schedule](#)”;

Proprietary confidential information © 2020 Boehringer Ingelheim International GmbH or one or more of its affiliated companies

10. Continuous ECG monitoring to be done starting at least 15 minutes pre-dose of BI 894416 or placebo administration and for at least 4 hours following BI 894416 or placebo administration (3-lead ECG recording).
11. This sample is optional. In case a patient takes part in both a SRD and a MRD dose group only one pharmacogenomic sample is to be taken. The pharmacogenomics sample requires a separate consent.

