12. PK samples for plasma level determination of BI 894416 [REDACTED] assay are to be taken at the time points as outlined in Flow Chart “[SRD part – Time schedule](#)” and in [Section 5.3.2.2](#) Sampling times and periods may be adapted based on information obtained during the trial (e.g. preliminary PK [REDACTED]) including addition of samples and visits as long as the total blood volume taken does not exceed 500 mL per patient.
13. PK urine samplings for determination of BI 894416 amount eliminated in urine are to be taken at following time intervals: A blank urine sample is to be obtained within 3 hours prior to administration of trial medication. Other urine samples are to be collected over the stated post-dose intervals 0-4, 4-8, 8-12, 12-24 and 24-48 h (see Flow Chart “SRD part – Time schedule”; [Section 5.3.2.3](#)).
14. AEs and concomitant therapies will be recorded throughout the trial, but will be specifically asked at time points indicated in the Flow Chart “SRD part – Time schedule” below.
15. 12-lead ECG and rhythm strip over at least 15 min.
16. Safety laboratory to be taken and to be medically evaluated within 3 days (within 76 hours) prior to administration of BI 894416; this ambulatory visit including safety laboratory, neurological exam, ECG and adverse event questioning can be omitted if the screening examination is performed on Day -3, [Tables 5.2.4: 1](#) and [5.2.4: 2](#).
17. Three triplicate ECGs are recorded within approximately one hour. The recordings should be separated by at least 15 minutes (refer to Flow Chart “SRD part – Time schedule” and [Section 5.2.5.1](#)).
18. All ECGs at this day will be done as triplicate ECG (for details refer to SRD part – Time schedule and Section 5.2.5.1).
19. Oral with 240 mL of water after an overnight fast of at least 10 h. (please also refer to [Section 4.2.2.2](#))
20. Physical examination includes an echocardiography (stress) test in the screening period in patients aged 45 and older.
21. SARS-CoV-2 PCR Test will be done at Visit 2 only. Result must be available prior to randomization. If Visit 2 is omitted (see [footnote 16](#)), the test must be performed on day -3 to -1.

SRD PART – TIME SCHEDULE

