15. PK urine samplings for determination of BI 894416 amount eliminated in urine are to be taken at following time intervals: A blank urine sample is to be obtained within 3 hours prior to administration of trial medication. [REDACTED] Other urine samples are to be collected over the stated post-dose intervals 0-4, 4-8, 8-12 and 12-24h after BI 894416 or placebo administration on Day 1 and Day 9 only.
16. AEs and concomitant therapies will be recorded throughout the trial, but will be specifically asked at time points indicated in the Flow Chart “MRD part – Time schedule”.
17. Safety laboratory to be taken and to be medically evaluated within 3 days (within 76 hours) prior to administration of BI 894416; this ambulatory visit for safety laboratory and questioning for AEs and concomitant therapies can be omitted if the screening examination is performed on Day -3 or if lab sample can be taken on Day -1 and the lab results can be medically evaluated before BI 894416 or placebo administration at Day 1, [Tables 5.2.4: 1](#) and [5.2.4: 2](#).
18. Three triplicate ECGs are recorded within approximately one hour. The recordings should be separated by at least 15 minutes (refer to Flow Chart “MRD part – Time schedule” and to [Section 5.2.5.1](#));
19. Triplicate ECG (refer to Flow Chart “MRD part – Time schedule” and to Section 5.2.5.1);
20. Oral with 240 mL of water after an overnight fast of at least 10 h; (please also refer to [Section 4.2.2.2](#))
21. Oral with 240 mL of water

Proprietary confidential information © 2020 Boehringer Ingelheim International GmbH or one or more of its affiliated companies

- ^{22.} Physical examination includes an echocardiography (stress) test in the screening period in patients aged 45 and older. Assessment can be omitted if patient took part in one of the SRD groups before.
- ^{23.} SARS-CoV-2 PCR Test will be done at Visit 2 only. Result must be available prior to randomization. Result must be available prior to randomization. If Visit 2 is omitted (see [footnote 17](#)), the test must be performed on day -3 to -1.

MRD PART / TIME SCHEDULE

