5.2.4 Safety laboratory parameters

For the assessment of laboratory parameters, blood and urine samples will be collected by the trial site at the time points indicated in the Flow Charts after the patients have fasted for at least 10 h. Overnight fasting is not required at the discretion of the investigator or designee for retests or drug screening.

The parameters that will be determined are listed in [Tables 5.2.4: 1](#) and [5.2.4: 2](#). Reference ranges will be provided in the ISF, Section 10.

Manual differential white blood cell count or urine sediment examinations will only be performed if there is an abnormality in the automatic blood cell count or in the urinalysis, respectively.

Table 5.2.4: 1 Routine laboratory tests

Functional lab group	BI test name [comment/abbreviation]	A¹	B¹	C¹
Haematology	Haematocrit Haemoglobin Red Blood Cell Count (RBC) Reticulocytes (relative and absolute) White Blood Cells (WBC) Platelet Count/Thrombocytes (quant)	X X X X X X	X X X X X X	X X X X X X
Automatic WBC differential, relative and absolute Manual differential WBC (if automatic differential WBC is abnormal)	Neutrophil; eosinophils; basophils; monocytes; lymphocytes Polymorphnuclear neutrophils (segs), band neutrophils (stabs), eosinophils, basophils, monocytes, lymphocytes	X	X	X
Immunoglobulins in serum	IgA IgD IgE, total and specific IgG IgM	X X X X X	-- -- -- -- --	X X X X X
Lymphocyte differentiation (relative and absolute; except for ratio)	T cells (CD3+), T helper cells (CD3+CD4+), cytotoxic T cells (CD3+CD8+), B cells (CD19+), natural killer cells (CD16+CD56+CD3-), CD4:CD8 ratio	X	--	X
Coagulation	Activated partial thromboplastin time (aPTT) Prothrombin time (Quick's test and INR)	X X	X X	X X
	Platelet Function (via Platelet Function Assay)			See below
Enzymes	AST [Aspartate transaminase]/GOT, SGOT ALT [Alanine transaminase]/GPT, SGPT Alkaline phosphatase (AP) Gamma-glutamyl transferase (GGT) Creatine kinase [CK]; CK-MB only if CK is elevated] Lactate dehydrogenase Lipase Amylase	X X X X X X X X	X X X X -- -- -- --	X X X X X X X X
Hormones	Thyroid Stimulating Hormone (TSH)	X	--	--
Molecular Diagnostics	PCR test for the detection of SARS-CoV-2		X	
Substrates	Plasma glucose Creatinine Total bilirubin Direct bilirubin Total protein C-Reactive Protein (CRP) Uric acid Total cholesterol Triglycerides	X X X X X X X X	X X X X -- X -- --	X X X X X X X X
Electrolytes	Sodium Potassium Calcium Inorganic phosphate	X X X X	X X X --	X X X X

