6.7 BASELINE, TIME WINDOWS AND CALCULATED VISITS

The baseline value is defined as the last measurement before first administration of BI 894416 (SRD part: value at V3, ptm -3:00, MRD part: value at V3, ptms -17:00, -1:00, -0.05).

Section 6.1 of the CTP: *Exact times of measurements outside the permitted time windows will be documented. The acceptable time windows for screening and the end of trial examination are provided in the CTP Flow Charts.*

If Screening Visit is performed on Day -3 (within 76 hours) prior to administration of trial drug, the ambulatory Visit 2 can be omitted.

Study measurements and assessments scheduled to occur ‘before’ trial medication administration on Day 1 are to be performed and completed within a 3 h-period prior to the trial drug administration (including blank values for PK and biomarkers).

In the SRD part, the acceptable deviation from the scheduled time for vital signs, ECG, and laboratory tests will be ± 15 min for the first 4 h after trial drug administration, ± 30 min thereafter on Day 1 and ± 90 min on Day 2.

The acceptable deviation from the scheduled time for neurological tests in the SRD part is ± 45 min on Day 1 and ± 90 min on Day 2.

Starting from 48 h post administration a time window of ± 120 min will be allowed for all study activities (incl. PK and biomarker sampling) in the SRD part.

In the MRD part, the acceptable deviation from the scheduled time for vital signs, ECG, and laboratory tests will be ± 15 min for the first 4 h after trial drug administration on Day 1

and Day 9, ± 30 min thereafter on Day 1 and Day 9, ± 90 min on Day 2 and on Day 10 and ± 120 min from Day 11 onwards.

The acceptable deviation from the scheduled time for neurological tests in MRD part is ± 4 min on Day 1, and ± 90 min on Day 2.

From Day 3 until Day 8 and from 48 h post last administration on Day 9 a time window of ± 120 min will be allowed for all study activities (incl. PK and biomarker sampling) in the MRD part, except PK samples taken pre dose on Days 5, 7 and 8. Pre dose PK samples are taken within a time window of 15 min prior to drug administration.

Adherence to time windows will be checked via the consistency check listings at the RPM/DBLM.

If Visit 2 is omitted because Visit 1 was performed within 76 hours prior to the trial drug administration, the Visit 1 ECG data were transferred as Visit 2 data.

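### SAP 6.6 fills a missing laboratory baseline from screening (up to 28 days before dosing) even for parameters measured again within 76 hours before dosing

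*SAP*

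**What the plan says.** **Imputation rule.** SAP 6.6: "Missing baseline laboratory values will be imputed by the respective values from screening". No visit is named. SAP 4 announces this imputation as a departure from CTP 7.5.1, which planned none for safety parameters. Earlier in SAP 6.6, however, AE dates are described as the only safety data for which imputation might be needed.

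**Baseline definition.** SAP 6.7: "The baseline value is defined as the last measurement before first administration of BI 894416 (SRD part: value at V3, ptm -3:00". The parenthesis goes on to name three Visit 3 time points for the MRD part.

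**Pre-dose laboratory samples.** Visit 1, labelled screening in the flow charts, falls on Day -28 to Day -3. Visit 2 falls on Day -3 to Day -1, and footnote 16 of the SRD overview (footnote 17 in MRD) reads: "Safety laboratory to be taken and to be medically evaluated within 3 days (within 76 hours) prior to administration of BI 894416". Visit 2 "can be omitted if the screening examination is performed on Day -3" and, in the MRD part only, "or if lab sample can be taken on Day -1 and the lab results can be medically evaluated before BI 894416 or placebo administration".

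**Content of the samples.** "Letters A, B, and C describe different sets of safety laboratory examinations" (SRD overview, footnote 6). In the SRD part Visit 1 is set A, Visit 2 is set B and the Day 1 pre-dose sample is set C.

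**The concern.** When the Visit 3 value is missing, the usual substitute is the nearest earlier pre-dose value. SAP 6.6 instead sends the programmer to screening, which on its usual meaning in these documents is the oldest sample available. For any parameter measured again shortly before dosing, that passes over a better value. It also sits badly with the principle in SAP 6.7 that baseline is the last measurement before the first dose.

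At stake are the laboratory change and percent-change summaries in SAP 7.8.2. An older starting point lets changes over the weeks before treatment enter what is presented as change on treatment. Active groups are planned at 8 patients, so a single affected patient has visible weight in a group mean.

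**Working it through.** No sample size or test is involved. The check is a comparison of visit timing and laboratory content.

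**Step 1: age of the substitute value.** The SRD time schedule equates Day -3 with -72:00, so one day counts as 24 h.
- Oldest Visit 1 value: 28 × 24 = 672 h before dosing.
- Oldest sample under the pre-dose laboratory requirement: 76 h.
- Ratio: 672 / 76 = 8.8.

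**Step 2: is a later sample always scheduled?**

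| Situation | Nearest scheduled sample before Day 1 | Does the screening rule lose anything? |
|---|---|---|
| Screening on Day -3, Visit 2 omitted | Visit 1, within 76 h | No |
| Screening earlier, Visit 2 held | Visit 2, within 76 h | Yes, for parameters in that sample |
| MRD, Visit 2 replaced by a Day -1 sample | Day -1 | Yes, for parameters in that sample |

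So whenever the Visit 1 value is older than 76 h, the protocol requires a later pre-dose sample. The SAP does not say whether an MRD Day -1 sample could already count as a Visit 3 value under the -17:00 time point in SAP 6.7.

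**Step 3: which parameters does the later sample cover?** From protocol Table 5.2.4: 1:
- In set B: haematology, automatic white-cell differential, coagulation, AST, ALT, AP, GGT, creatinine, sodium, potassium and calcium.
- In sets A and C but not B: immunoglobulins ("IgA IgD IgE, total and specific IgG IgM"), lymphocyte subsets, CK, LDH, lipase, amylase, inorganic phosphate and urinalysis.
- The substrates row is broken in the text available to me (nine names, eight marks). I rely on it only for creatinine, which is marked in set B however the marks are aligned.
- The set taken at MRD Visit 2 is not legible in that text.

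For SRD set B parameters, the maximum age of the substitute would fall from 672 h to 76 h under a most-recent-value rule. For SRD parameters outside set B it stays at 672 h, because Visit 1 is the only earlier scheduled sample.

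**Step 4: weight of one patient.** In a group of 8, one patient carries 1/8 = 12.5% of the mean. If the Visit 1 and Visit 2 values differ by d, choosing one over the other shifts the group mean change by d/8. The documents give no value for d and no rate of missing baselines.

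**The case against.** **Screening may be meant broadly.** CTP 7.3.4 assigns every measurement planned before first intake to the screening period, and SAP 6.1 runs the screening phase for AEs up to first administration. Both would include Visit 2. This stands as a possible reading, but it does not rescue the rule: two samples would then qualify and SAP 6.6 would not say which to use. The narrower meaning is also the more natural one. The flow charts label Visit 1 as screening, SAP Table 6.7: 1 (an ECG table) calls Visit 2 pre-treatment, and CTP 6.1 distinguishes the screening visit from the ambulatory Visit 2.

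**SAP 6.6 and 6.7 need not contradict each other.** A reader might infer two rival baseline definitions. The parenthesis in SAP 6.7 ties baseline to Visit 3, so SAP 6.6 can be read as the fallback when that value is missing. That objection stands. What remains is that the fallback does not follow the principle of the definition it supports.

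**A later value does not exist for every parameter.** This also stands. For the immune-monitoring tests and the others outside set B, falling back to Visit 1 is reasonable in the SRD part.

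**Stronger claims about size.** A reader might infer that Visit 1 is unsuitable because it precedes the alcohol restriction. That restriction starts 48 h before dosing and SRD Visit 2 is planned at -72:00, so it does not separate the visits. A reader might also infer a several-fold larger variance of change, but any such figure rests on within-person correlations that neither document gives.

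**Little depends on it.** The primary endpoint is drug-related AEs, the hepatic events of special interest use multiples of ULN, laboratory analyses are descriptive, and individual values are listed. This stands and sets the weight of the point.

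**Conclusion.** The point holds as a minor flaw in the choice of rule. On the natural reading, SAP 6.6 prefers a laboratory value up to 28 days old to one scheduled within 76 hours of dosing, for those parameters the later sample contains. On the broad reading, it leaves the choice undefined. The documents do not support saying that a Visit 2 value exists for every parameter, or that SAP 6.6 flatly contradicts SAP 6.7.

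The effect is limited to descriptive laboratory change-from-baseline summaries for patients with a missing Visit 3 value, presumably few since dosing and sampling take place at the site under supervision. Its size cannot be computed from the documents. The conclusion assumes that the required pre-dose sample was taken and its values are usable.

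**What to change.** Replace the SAP 6.6 sentence with one on these lines:

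> A missing baseline laboratory value is replaced, per parameter, by the most recent non-missing value before first administration (Visit 2 or Day -1 if measured there, otherwise Visit 1).

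The per-parameter wording matters: it leaves Visit 1 as the source for tests outside set B. In the same edit, amend the statement in SAP 6.6 that AE dates are the only safety imputation, so that it agrees with this rule and with SAP 4. The cost is two sentences of text and a small change to the baseline derivation; no extra data are needed.
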